5.7 Withdrawal of Subjects

After participants sign both the HIPAA and Informed Consent documents, officially enrolling them in the study, they will be screened for cognitive impairment with the MMSE questionnaire before starting baseline data collection. Those who score ≤ 23 will immediately be withdrawn from the study, and their PCPs will be alerted.

Participants are able to withdrawal at any time without consequence by either alerting the RC or the investigator. They will be able to keep the payment(s) they have already received but will not receive additional payment. UC participants can continue or discontinue care at their discretion. ABC care participants will no longer be treated as part of the study but can be referred to an ABC clinic by their PCP to re-engage treatment. Follow-up calls will be terminated, discontinuing data collection. Previously collected data will still be analyzed.

6 Reporting

The overall PI and the overall RC will be available on a daily basis to take calls and emails from all study-site personnel. In addition, teleconferences will be scheduled at the site PI's discretion to discuss goals, progress, modifications, documentation, recruitment, retention, data analysis, and confidentiality. Any instances of adverse events, protocol deviations, or other problems identified during the meetings

will be reported as soon as possible within the required reporting timeframes using the standard forms and/or procedures set forth by the IRB. In addition, clinical coordinators may review study documentation and/or consent forms to ensure that subject's confidentiality is maintained.

7 Privacy and Confidentiality

Protected Health Information (PHI) will be used for the purposes of contacting the subject via telephone and mail, as well as to screen their CPRS records. PHI will not be used outside of these few functions, nor will it be disclosed or used on any data collection measures.

[figure not shown]
All data will be collected on hard copies and stored under double lock and key in the research team members' office and/or file cabinets. No members outside of the research team will have access to this information. Data will be entered into an electronic database created in Microsoft Access, specifically for the purposes of this study. No PHI will be kept in this database. All electronic data and information will be kept on a protected VA shared drive that only research team members will have access to. Also, a master list of all subjects who have signed Informed Consent documents will be kept electronically on the VA Shared Drive.

Study subjects will be assigned unique identifiers that will appear on all files used in the statistical analyses; all data will be de-identified. Only limited team members at participating VAs will have access to personal information needed for tracking and informed consent. Several steps will be taken to ensure data quality and data integrity: 1) use of standard methods of data collection and recording specified in a manual of operations 2) required viewing of a webcast staff workshop on research integrity and data entry at the beginning of the study and when new personnel are hired, and 3) audits on a random sample of participants to verify completion of interviews and data accuracy. A code number will be the only identifier on the electronic data that is stored on a protected VA Shared Drive. There will be no data fields in which to enter PHI electronically.

All research desktop computers will be encrypted. The encryption software will be Federal Information Processing Standards (FIPS) 140-1,2 compliant. Data will be kept on the protected VA Shared Drive at least 3 years following completion of the study and will be archived to ensure compliance with VHA regulations forbidding the destruction of research records.

8 Communication Plan

The within and between site communication structure is shown in the diagram below.

Within and Between Sites Communication Structure

The Overall PI and Overall RC, located at VAPHS, will have ongoing communication throughout the duration of the study. The Overall PI and the Local Site PIs also will maintain an open line of communication for the duration of the study, as will the Overall RC and the Local Site RCs, and the Local Site PIs and the Local Site RCs. We expect site personnel to respond to each other within 24 hours, preferably with the same day.

The ABC Clinic operations will be overseen by the Local Site PI and the Local Site RC. The RC will be responsible for maintaining the clinic schedule (i.e., scheduling all appointments and any changes to the schedule). The Local Site PI will be the ABC Clinic Director. The RC will schedule appointments with the ABC clinic providers and ensure that those assigned to UC do not have appointments with the ABC providers for the duration of the study. Day to day procedures for operationalizing this process will be finalized during the study start-up period at each site.

Communication also will occur between ABC Clinic Providers and other relevant clinic providers that are consulted in the context of the algorithms. This will occur in the same manner as per standard VA care. That is, consultations will be ordered through CPRS and all patient-related communications will occur securely through CPRS.

Recurring Meetings

The Overall PI and the Overall RC will meet weekly to discuss overall and site-specific activities, including recruitment, enrollment, retention, and any additional study activities or concerns. Additional meetings will be conducted as the need arises. The RC will take notes and keep those records for the duration of the study.

The Overall PI, Overall RC, Local Site PIs and RCs will meet weekly via teleconference during project start-up and the first six weeks of recruitment. Then, meeting frequency will be monthly or as needed for the duration of the project. During the first three months of recruitment, they will discuss recruitment strategies, progress, and ensure adherence to the protocol. For the duration of the study, the calls will focus on responding to local site PI/RC questions, discussing recruitment goals and actual recruitment, as well as retention, enrollment, and follow-up progress. Notes will be taken by the Overall RC and kept for the duration of the study.

The Overall PI, the Local Site PIs, and all ABC clinic providers will communicate during regularly scheduled meetings. During project start-up, the Overall PI will meet with the Local Site PIs and ABC clinical providers to review 2-3 algorithms per week. During the first 6 weeks of participant enrollment, weekly meetings will continue, and specific participant cases will be discussed. Providers will present cases which allow for discussion on adherence to and reinforcement of the published algorithms. Subsequently these meetings will occur monthly or on an ad hoc basis.

Local Site PI, the local site ABC Clinic Providers, and the Site RC will meet weekly or as needed to ensure that the procedures discussed during the meetings with the Overall PI and Overall RC are followed. They will discuss any site-specific clinical and administrative issues that arise, including but not limited to recruitment, enrollment, retention, follow up, flow of the study, and adherence to the protocol. Local RCs will take notes and keep them for the duration of the study.

Any instances of adverse events, protocol deviations, or other problems identified during the above meetings will be reported as soon as possible within the required reporting timeframes using the standard forms and/or procedures set forth by the IRB.

A summary of the project meetings is provided in the table below.

Within and Between Site Communication

Communication Level and Participating Staff	Communication Frequency		Meeting Focus
	Start-up period	Post-startup and following	
Overall: PI and RC	Weekly	Weekly	Track overall study progress and procedures
Overall with Local Sites: Overall PI/RC, site PIs and site RCs	Weekly	Monthly or as needed	Track site-specific study progress and procedures
Overall with Local Sites: Overall PI, Site PIs, and ABC clinic providers	Weekly	Monthly or as needed	Discuss active cases in ABC arm
Within Site: Site PI/RC and ABC Clinic Providers	Weekly	Weekly or as needed	Team discusses site-specific study activities, both clinical and administrative

REFERENCES

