5.6 Data Analysis

Data Management: A summary of the baseline and follow-up data is provided in Table 7. Data will be collected using paper forms. Completed data forms will be entered into a secure electronic database on a VA network server with regular server backup. The PI will work with the VAPHS research team to oversee all aspects of data management in accordance with policies and procedures outlined in VHA Handbook 1200.12. Only research team members at participating sites will have access to personal information needed for conducting informed consent procedures and participant tracking. Data collected on paper forms and any identifiable information will be stored in the Research Coordinator's office at each site, under double lock and key. All participants will be assigned unique synthetic identifiers that will appear on forms, files and serve as a non-identifiable index in database tables. Only de-identified data will be entered into the secure electronic database. There will be no data fields in which to enter individually identifiable information electronically, except the synthetic participant study IDs. Data entry will include double data entry checks. All research desktop computers will be encrypted. The encryption software will be Federal Information Process Standards (FIPS) 140-1,2 compliant. Data collected for this study will be kept in compliance with VHA regulations forbidding the destruction of research records.

Data Analysis:

Overview:

The study Statistician, [name] will be in charge of data analysis along with the PI. [name] will be sent only de-identified data as described above. We will perform all main analysis based on **intention-to-treat** following the a priori plans outlined

Table 7. Baseline and Follow-up Data

Measure	Timepoint		
	Baseline	Q3 month*	Q month
Oswestry Disability Index (Primary Outcome)	X	X	
NIH Task Force Minimum Data Set	X		
Quick Mild Cognitive Impairment (QMCI) screen	X		
Medical Comorbidity (Duke Comorbidity Index)	X		
Social Support (MOS Social Support Scale)	X		
Prescribed Opioids Difficulties Scale	X		
Pain Self Efficacy Questionnaire	x		
Gait Speed	X		
Life Space Assessment	X	X	
0-10 Numerical Rating Pain Scale	X	X	X
PROMIS-29	X	X	
Falls Efficacy Scale-international Short Form	X	X	
PROMIS Global Health Scale	X	X	
Veterans RAND 12 Item Health Survey (VR-12)	X	X	
Treatment History	X		
Healthcare Utilization (pain medication, emergency room use, hospitalization)	X	X	X
Medications	X		final month

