The goal is to explore whether ABC vs UC differences in improvement vary across participant subgroups of interest (effect modification). We will add each of the subgroups (based on baseline CLBP-associated disability, anxiety/ depression, mild cognitive impairment and obesity) and associated subgroup \times intervention group interaction effects as additional fixed effects in the above statistical models. Rigorous methodological guidelines for subgroup analyses require significant interaction effects for making conclusions of differential intervention effects in subgroups.⁹⁹ As such, we will first construct difference-in-difference type means contrasts representing the difference in ABC vs UC effects in different subgroups at each of the follow-up time points. If and only if the said interaction contrast is significant, we will estimate ABC vs UC differences and

their statistical significance within those subgroups.

Missing Data:

The best approach for handling missing data is to prevent it. We will use the methods described earlier to retain participants and prevent missing data. Despite our best efforts, missing data will occur. We will clearly document those with missing data and reasons in the CONSORT diagram, and compare those with missing data to complete data with respect to available data. Statistical guidelines for handling missing data recommend methods such as multiple imputation, which considers the uncertainty involved in imputing missing data.¹⁰⁰ Multiple imputation is arguably the best available objective method to analytically account for missing data under the ignorable or missing-at-random (MAR) assumption. Specifically, we will generate M=5 imputed values for each missing value, analyze the 5 datasets as though complete, and finally combine the results appropriately so that they reflect the uncertainty involved in imputation. SAS® MI and MIANALYZE procedures will be used. Other approaches to missing data, including the naïve approaches of ignoring the missing values and last-value-carried-forward (LVCF) will also be considered in sensitivity analyses and robustness of the results to using these approaches will be examined.

Sensitivity Analyses:

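### Section 5.7 gives no explicit option to stop ABC care while keeping the outcome calls, so ODI data may be lost avoidably and unevenly by arm

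*Combined protocol and SAP*

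**What the plan says.** Apart from exclusion on the cognitive screen, Section 5.7 has one withdrawal route, which starts when the participant notifies the coordinator or investigator. Its consequences are listed together:

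- For the ABC arm: "ABC care participants will no longer be treated as part of the study but can be referred to an ABC clinic by their PCP".
- For the UC arm: "UC participants can continue or discontinue care at their discretion".
- For outcomes: "Follow-up calls will be terminated, discontinuing data collection".
- For data already in hand: "Previously collected data will still be analyzed".

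Section 5.6 (Data Analysis, Overview) bases the main analyses on "intention-to-treat". Section 5.6 (Missing Data) opens with "The best approach for handling missing data is to prevent it". It then specifies five multiple imputations under missing at random (MAR), with two alternatives as sensitivity analyses: ignoring missing values and last value carried forward (LVCF).

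Section 5.5 (Follow-up) collects the ODI by quarterly telephone call, timed from randomization. The example given has a coordinator at a different site making the call. Section 5.5 also leaves the frequency of ABC visits open, lets the provider record compliance as none, and tracks attendance in both arms. It does not tie non-attendance to withdrawal.

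**The concern.** Leaving a multi-component clinic programme and refusing a quarterly telephone call are different decisions, and Section 5.7 does not separate them. When a participant says that they want to stop ABC care, the only written procedure closes outcome collection as well. Nothing practical requires this, because the calls do not depend on clinic attendance.

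An intention-to-treat comparison is strongest when outcomes are collected whatever treatment was received. The retention measures in Section 5.5 are payments, reminder letters and post-study ABC care for the UC arm. None addresses people who leave treatment.

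The loss may also be uneven. A UC participant has no study treatment to give up, whereas an ABC participant who is not improving does. If such people leave follow-up, MAR imputation may fill in values that are too favourable for them. The plan does not list the imputation variables, and the primary model uses only 6 and 12 months. It is therefore not known whether a poor 3-month ODI would inform the imputed 6-month value.

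**Working it through.** **1. Is stopping ABC care the same as withdrawing?** No text says so. Section 5.7 lists loss of study ABC care as a consequence of withdrawal, not as its trigger. Under Section 5.5, someone who stops attending without saying so remains due for calls. The gap therefore concerns the participant who tells staff that they want to stop.

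**2. The plan's own power figure.** Inputs from Section 5.6 (Sample Size Justification): SD of ODI change 18, difference 7, two-sided alpha 0.05, 310 randomized, 280 completers, stated power 90%. Allocation is 1:1 (Section 5.5).

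SE = 18 × √(1/n₁ + 1/n₂); power ≈ Φ(7/SE − 1.96).

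- 280 completers: SE = 18 × √(4/280) = 2.151; 7/2.151 − 1.96 = 1.294; power 0.902. The stated 90% is reproduced.
- The stated 15% dropout leaves 310 × 0.85 = 263.5, or about 264: SE = 2.218; power 0.884. The plan's 280 implies 1 − 280/310 = 9.7% dropout. That is a separate inconsistency; the 15% figure is used below.
- All 310 observed: SE = 2.045; power 0.928.

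**3. Power gained by the change.** Assume 15% loss in each arm, with half of the ABC loss recovered because those people would still take calls.

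- ABC: 155 × (1 − 0.075) = 143.4. UC: 155 × 0.85 = 131.75. Total about 275.
- SE = 18 × √(1/143.4 + 1/131.75) = 2.172; 7/2.172 − 1.96 = 1.262; power about 0.897.

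Power rises from about 0.88 to about 0.90. This holds the difference at 7 points after the recovered participants are included.

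**4. Possible bias.** Let f be the share of the ABC arm lost to follow-up and k the number of points by which their true mean change is worse than the imputed value. With no matching shortfall in UC, the contrast is overstated by f × k. The documents give neither quantity, so both are assumed.

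| f | k = 3 | k = 5 | k = 7 |
|---|---|---|---|
| 5% | 0.15 | 0.25 | 0.35 |
| 10% | 0.30 | 0.50 | 0.70 |
| 15% | 0.45 | 0.75 | 1.05 |

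The range is 0.15 to 1.05 ODI points, or 2% to 15% of the 7-point target (0.15/7 and 1.05/7).

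**5. Would a planned analysis show it?** Not directly. MAR imputation assumes it away. Ignoring missing values relies on those who remain. LVCF touches the scenario when a leaver's last value is poor, but it does not vary the assumed outcome of ABC leavers.

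**The case against.** Section 5.7 governs withdrawal from the study, and ending contact with someone who withdraws does not contradict analysis by assigned arm. Earlier data are kept, missing values are imputed, and reasons for missingness are to be documented. UC participants may leave too, for example from disappointment at their allocation, and nothing shows that ABC losses will be larger. Retention measures exist, and Pilot Study #2 reported no dropouts among 50 enrolled, although its follow-up was not complete. LVCF partly probes the case of the non-improving leaver, and MAR imputation can condition on earlier ODI values. The consent pages were not available, so partial withdrawal may already be offered there.

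Much of this stands, and it rules out some stronger readings. A reader might infer that anyone who stops ABC care has no way to keep giving outcomes. Section 5.5 does not support that, because non-attendance alone does not end the calls. A reader might also infer that the intention-to-treat analysis is defeated. It is made less complete, and the safeguards reduce the harm. They do not replace outcomes that could have been collected, and they leave the wording of 5.7 as it is.

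**Conclusion.** The point holds as a gap in Section 5.7. A participant who asks to stop ABC care is given no explicit option to stay in outcome follow-up, and the written procedure may lead staff to end calls that could have continued. That sits badly with the intention-to-treat aim and with the plan's own priority of preventing missing data.

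The power effect is small: about 0.88 to about 0.90 if half of a 15% ABC-arm loss is recovered. A reader might claim more by recovering half the loss in both arms (310 × 0.925 = 287 completers, power about 0.91). That does not follow from an argument about stopping a treatment that only one arm has.

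Possible bias is the stronger reason to act: about 0.15–1.05 points on the assumed ranges. That it favours ABC is plausible but assumed; a matching shortfall in UC would offset it. A reader might infer a larger bias by blaming the whole trial dropout on this rule and assuming strongly response-driven exits. The documents do not say how much of the 15% is withdrawal, or why people would leave, so they do not support a firm larger figure.

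**What to change.** In Section 5.7, and in the consent form if it does not already say so, define two levels:

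- **(a) Stops ABC visits, continues outcome calls.** Ask about this explicitly and treat it as the default. If burden is the reason, offer a call limited to the ODI.
- **(b) Withdraws from all contact.**

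End calls only for (b), record the level and the reason, and include all level (a) data in the intention-to-treat analysis. Participants at level (b) will still have missing outcomes. A delta-adjusted sensitivity analysis, which makes the imputed ABC values progressively worse, would be a useful optional addition.

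The cost is protocol wording, possibly consent wording, and continuing calls that are already planned. No treatment rule changes, and participants remain free to refuse all contact.
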